Study protocol

Official title: Are neuroticism, perceived stress, and adverse life events risk factors for functional somatic disorders?

DanFund

Background

Functional somatic disorders (FSD) are common disorders with a multifactorial aetiology involving biological, social, and psychological factors (1, 2). An often used explanation of the illness mechanisms behind FSD which is provided to the patients is, that FSD may be understood as a multi systemic physical response to stress (3). This relationship can be modelled as proposed in the Cognitive Behavioural Therapy (CBT) model of emotional distress where several cognitive, behavioural and psychological factors are thought to contribute to the onset and perpetuation of FSD (4). in the Cognitive Behavioural Therapy (CBT) model of emotional distress where several cognitive, behavioural and psychological factors are thought to contribute to the onset and perpetuation of FSD. Personality traits e.g. neuroticism contribute to give rise to our cognitive, behavioural, and psychological reactions. Furthermore, neuroticism with its heightened reactivity to stressors, has shown to be an important predictor of a generic vulnerability to both physical and psychological conditions. Having been exposed to previous adverse life events/traumas and childhood adversities has also showed to impact the risk of having FSD. This relationship has been proposed to be induced by a heightened response to stimuli, i.e. sensitisation, caused by physical and emotional distress triggering a hormonal cascade in the hypothalamus pituitary adrenal (HPA) axis (4, 5).

So far, most studies into these aspects have been carried out in selected patient samples, and general population-based studies including a large randomly obtained are sparse. In three recent population-based studies, we have established strong associations between FSD and neuroticism, perceived stress, and the accumulated number of experienced adverse life events (ALE), respectively (6). However, these studies were cross-sectional, thereby not providing insight to whether these factors were risk factors of FSD. More studies are needed for further elucidation on these aspects.

Objective

The objective of this study is to explore the role of neuroticism, perceived stress, and the accumulated number of ALE, respectively, in the development and perpetuation of FSD.

Hypotheses

1) Higher neuroticism, higher perceived stress, and higher number of ALE at baseline are individual risk factors of having developed FSD in the 5-year period from baseline to follow-up:

FSD non-case at baseline → FSD case at follow-up

2) Neuroticism, perceived stress, and the accumulated number of ALE positively contribute to the perpetuation of FSD from baseline to follow-up:

FSD case at baseline → FSD case at follow-up

Methods

Study population

Data from the DanFunD (Danish Study of Functional Disorders) baseline and 5-year follow-up investigation cohorts will be included (7, 8). The baseline cohort (gathered in the years 2012-2015) is a random sample selected through the National Civil Registration system among people living in 10 municipalities in the western part of greater Copenhagen, Denmark, ages 18 to 76 years. The baseline cohort constitutes data from self-reported questionnaires (n=7,493) and diagnostic interviews data (n=1,590). The follow-up cohort (gathered in the years 2018-2020) consists of participants all born in Denmark, between 24 and 84 years of age. The follow-up cohort constitutes data from self-reported questionnaires (n=4,288) and diagnostic interviews data (n=1,094).

Primary outcome (dependent variables):

Preferably, if a sufficient number of incident and perpetuating cases are available at follow-up, participants with FSD will be defined as follows:

- Participants fulfilling the criteria of the unifying diagnostic concept Bodily Distress Syndrome single- and multi-organ type will be defined with both questionnaires (9) and diagnostic interviews (10, 11)

- Participants with irritable bowel, chronic widespread pain, and chronic fatigue will be defined with questionnaires (12-14)

Primary explanatory/independent variables:

All primary explanatory variables will be self-reported. Neuroticism will be measured with the Danish version of the short-form NEO Personality Inventory (NEO-PI-Rsf) (15). Perceived stress will be measured with the 10-item Cohen's Perceived Stress Scale (16). The accumulated number of ALE will be measured with the Danish version of the Cumulative Lifetime Adversity Measure (CLAM) (17).

Analytical plan

All analyses will be performed using STATA version 17.0 (18).

Descriptive statistics will be presented for all the three continuous explanatory variables across FSD diagnoses. Depending on data distribution, descriptive statistics will be presented as means and standard deviations or medians and interquartile ranges.

Depending on number of incident and perpetuating cases at follow-up, a range of analyses will be conducted with the purpose of investigating if higher neuroticism, higher perceived stress, and higher accumulated number of ALE at baseline

- 1) are individual risk factors for the development of FSD from baseline to follow-up
- 2) are positively contributing to the perpetuation of an FSD from baseline to follow-up

The first choice of analyses

For hypothesis one, multiple logistic regression models will be performed with incident FSD cases at follow-up as primary outcome and baseline neuroticism, perceived stress, and accumulated number of ALE as explanatory primary variables. The effect of neuroticism, perceived stress, and the accumulated number of ALE will be reported from the same analysis as the effect when controlled for the effect from the other primary explanatory variables. Odds ratio (OR) with 95% confidence intervals (CI) will be used as measure of association; an OR > 1 supports the hypothesis. The reference group will constitute participants without FSD at both baseline and follow-up. Reference value of neuroticism, perceived stress, and the accumulated number of ALE will be set as the median value of

the total sample. In each analysis there will be controlled for the confounding effect of sex (with male as reference) and age (the median value of the total sample).

For hypothesis two, multiple logistic regression models will be performed with FSD cases perpetuating from baseline to follow-up as primary outcome and baseline neuroticism, self-perceived stress, and accumulated number of ALE as primary explanatory variable. The effect of neuroticism, perceived stress, and the accumulated number of ALE will be reported from the same analysis as the effect when controlled for the effect from the other primary explanatory variables. Odds ratio (OR) with 95% confidence intervals (CI) will be used as measure of association; an OR > 1 supports the hypothesis. The reference group will constitute participants with FSD at baseline but without FSD at follow-up. Reference value of neuroticism, perceived stress, and the accumulated number of ALE will be set as the median value of the total sample. In each analysis there will be controlled for the confounding effect of sex (with male as reference) and (the median value of the total sample).

The second choice of analyses

If number of incident and perpetuated cases at follow-up are too low to perform the above multiple logistic regression models with incorporation of the three primary explanatory variables in one analyses per FSD definition, it will be investigated if the confounding primary explanatory variables can be reduced into one variable and incorporated in separate analyses instead. Hence, instead of performing one analysis per FSD definition, three logistic regression analyses will be performed for each FSD definition:

1. An analysis investigating the effect of baseline neuroticism (primary explanatory variable) as risk factor for incident FSD/contributor to perpetuating FSD (primary outcome) with adjustment for 1) perceived stress and the accumulated number of ALE reduced into one variable, 2) sex, and 3) age.
2. An analysis investigating the effect of baseline perceived stress (primary explanatory variable) as risk factor for incident FSD/contributor to perpetuating FSD (primary outcome) with adjustment for 1) neuroticism and the accumulated number of ALE reduced into one variable, 2) sex, and 3) age.
3. An analysis investigating the effect baseline accumulated number of ALE (primary explanatory variable) as risk factor for incident FSD/contributor to perpetuating FSD (primary outcome) with adjustment for 1) neuroticism and perceived stress reduced into one variable, 2) sex, and 3) age.

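### Each hypothesis concerns one outcome, FSD, but the primary outcome is five to seven equally ranked case definitions, with no deciding definition, case threshold or fallback

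*Combined protocol and SAP*

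**What the plan says.** The Hypotheses section makes two directional statements about a single outcome, functional somatic disorders (FSD). In the first, higher neuroticism, perceived stress and number of adverse life events (ALE) are "individual risk factors of having developed FSD in the 5-year period from baseline to follow-up". In the second, the same three factors "positively contribute to the perpetuation of FSD from baseline to follow-up". Under the first choice of analyses, an odds ratio (OR) above 1 supports the hypothesis. A 95% confidence interval (CI) is reported, but support is not made to depend on it.

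Methods, Primary outcome (dependent variables), then defines FSD by a list with a conditional lead-in: "Preferably, if a sufficient number of incident and perpetuating cases are available at follow-up, participants with FSD will be defined as follows". The list has two items:

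- "Bodily Distress Syndrome single- and multi-organ type will be defined with both questionnaires (9) and diagnostic interviews (10, 11"
- Three further conditions, each identified by questionnaire only: chronic fatigue, chronic widespread pain and irritable bowel.

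The definitions are analysed one by one and not as a composite. The second choice of analyses describes itself by contrast with the first: "instead of performing one analysis per FSD definition, three logistic regression analyses will be performed for each FSD definition". Each first-choice model yields three estimates: "The effect of neuroticism, perceived stress, and the accumulated number of ALE will be reported from the same analysis".

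The plan gives no number for a sufficient count and no alternative definition if the count is not reached. It does not rank the definitions or say how results are combined when they differ.

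**The concern.** A support rule needs an outcome to act on. Suppose the OR for perceived stress is above 1 for chronic fatigue and below 1 for interview-defined Bodily Distress Syndrome (BDS). A report that stress is a risk factor for FSD and a report that it is not would then be equally faithful to the plan. The plan calls BDS the unifying concept but gives it no precedence.

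The conditional lead-in adds a second freedom. Which definitions stand is settled after the follow-up case counts are known, against a threshold that is not written down.

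At stake is whether the question in the study's title gets an answer tied to an outcome fixed in advance.

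**Working it through.** The plan states no sample size, power or multiplicity figure, so there is none to reproduce. The check counts the ORs that compete to answer each question and then sizes the effect.

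**Inputs from the plan**
- BDS: 2 organ types by 2 instruments (questionnaire, interview).
- Other definitions: 3, by questionnaire only.
- Exposures: 3. Hypotheses: 2 (incidence, perpetuation).
- Interval: 95% CI. Support rule: OR above 1.

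**Step 1: number of definitions.** With organ types separate, 2 × 2 + 3 = 7. With organ types pooled within instrument, 2 + 3 = 5. The wording allows either reading.

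**Step 2: number of questions.** 3 exposures × 2 hypotheses = 6 separately named questions, each with 5 to 7 candidate ORs.

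**Step 3: chance of at least one supporting definition when the exposure has no effect.** Take a stricter rule than the plan's and require the 95% CI to lie wholly above 1, which has probability 0.025 per definition. With *k* independent definitions the chance is 1 − 0.975^*k*.

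| Definitions per question | Any CI wholly above 1 | Expected number |
|---|---|---|
| 1 | 2.5% | 0.025 |
| 5 | 1 − 0.975^5 = 11.9% | 5 × 0.025 = 0.125 |
| 7 | 1 − 0.975^7 = 16.2% | 7 × 0.025 = 0.175 |

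**Step 4: the plan's literal rule.** If any OR above 1 counts, each null OR has about a 50% chance. At least one of five then supports the hypothesis with probability 1 − 0.5^5 = 96.9%, and at least one of seven with probability 1 − 0.5^7 = 99.2%, again under independence.

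**Step 5: dependence between definitions.** The definitions are assessed in overlapping participants, so independence overstates the any-positive chance. The plan gives no correlation. Simulation of seven equally correlated test statistics (assumed values, 200,000 replicates, CI wholly above 1) gave:

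| Assumed correlation | Any of 7 |
|---|---|
| 0 | 16.2% |
| 0.3 | 13.7% |
| 0.5 | 11.5% |
| 0.7 | 8.9% |

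The expected number in Step 3 does not change with correlation.

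**The case against.** The strongest reply has four parts.

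**The aim is exploratory.** The Objective says the study will explore the role of the three factors, and parallel case definitions are a defensible choice in a population cohort. This softens the need for strict error control. It does not remove the gap, because the plan also states directional hypotheses, labels the outcome primary and sets a criterion for support.

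**The plan conditions on case counts, not on results.** Choosing definitions by count does not in itself favour those with an OR above 1. A reader might infer that the sponsor will keep or report only the favourable definitions. The documents do not support that: analyses are planned for each definition, and nowhere is reporting limited to one. The percentages above show how much room the plan leaves, not what it instructs.

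**The count can be inflated.** A reader might multiply 7 × 3 × 2 = 42 (or 5 × 3 × 2 = 30) and conclude that any one of 42 ORs can serve as the answer, with a 1 − 0.975^42 = 65% chance of a false finding. That goes too far. An OR for stress cannot answer the question about neuroticism, nor an incidence OR the question about perpetuation. The freedom due to the outcome definition is five- to sevenfold within each question.

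**Low counts are already handled.** The second and third choices of analyses are fallbacks for when the full model cannot be supported, and sparse definitions may be impossible to fit. This stands as a reason to keep those fallbacks. It also shows that a separate condition on the outcome is not needed, since the fallbacks change the model and leave the definitions in place.

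**Conclusion.** The concern holds. The hypotheses and the support rule refer to one FSD outcome, while the primary outcome is five to seven equally ranked definitions adopted subject to an unstated case count. Nothing says which one decides. For each of the six questions, mixed results could be reported as support or as non-support without departing from the plan.

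The size is up to a 12% to 16% chance of at least one supporting definition per question, against 2.5% with one deciding definition. This rests on three assumptions: no effect under any definition, a CI wholly above 1 as the criterion, and independence. The first is a benchmark and not an expectation, since the Background reports strong cross-sectional associations. The second is stricter than the plan's own rule. The third makes the figures upper illustrations.

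**What to change.** Before any model is fitted:

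1. **Name one deciding FSD definition, or a fixed hierarchy,** and state that each hypothesis is judged on it. BDS of either organ type by questionnaire is a reasonable candidate, because the plan calls BDS the unifying concept and follow-up has 4,288 questionnaires against 1,094 interviews. Those are all follow-up records, not cases. The documents do not rank the questionnaire above the interview, and the sponsor may choose interview-defined BDS.
2. **Say whether the organ types are pooled or separate,** so that the number of definitions is fixed.
3. **Label the remaining definitions secondary and report all of them.** Where even the fallback models cannot be fitted, give the case counts and say so.
4. **Replace the conditional lead-in** with a statement that low counts change only the model, through the second and third choices. Give a numeric event threshold for leaving the first choice. Low counts should not change which outcome decides the hypothesis.

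This reduces the deciding ORs from 30 to 42 down to 3 × 2 = 6, one per question. It does not settle multiplicity across those six, or whether an OR above 1 is enough without its CI; the plan should state its position on both.

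The cost is a few sentences and no new data. A pooled BDS outcome may add one model per hypothesis if the organ types were to be analysed separately. The real downside is that a favourable result in a secondary definition can no longer carry the hypothesis.

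### The plan says an odds ratio above 1 supports the hypothesis but gives the 95% confidence interval no stated part in that judgement

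*Combined protocol and SAP*

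**What the plan says.** Under The first choice of analyses, the same sentence appears once for hypothesis one (incident FSD) and once for hypothesis two (perpetuation): "Odds ratio (OR) with 95% confidence intervals (CI) will be used as measure of association; an OR > 1 supports the hypothesis". The Analytical plan introduces the analyses as being done "with the purpose of investigating if higher neuroticism, higher perceived stress, and higher accumulated number of ALE at baseline" are risk factors for developing FSD or contribute to its perpetuation.

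The hypotheses are directional. The first reads: "Higher neuroticism, higher perceived stress, and higher number of ALE at baseline are individual risk factors of having developed FSD", and the second posits a positive contribution to perpetuation. The Objective is worded more loosely: "The objective of this study is to explore the role of neuroticism, perceived stress, and the accumulated number of ALE, respectively".

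The document states no significance level, p-value, test, sidedness or condition on the interval. The second and third choices of analyses, used when cases are too few for the first-choice models, contain no statement of what counts as support.

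**The concern.** The sentence has two halves. The first makes the OR and its interval the measure of association. The second says what supports the hypothesis and names only an OR above 1. Read on its own terms, any point estimate above 1 is support, however imprecise.

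Two analysts following the text could therefore reach opposite conclusions from the same result. Take an invented OR of 1.2 with an interval from 0.9 to 1.6. One analyst reports support, because 1.2 is above 1. The other does not, because the interval includes values below 1. Both can claim to have followed the plan. What is at stake is how results are turned into conclusions, not the models, the data or the estimates.

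**Working it through.** **The plan's own figure.** There is none to reproduce, because the document gives no error rate, power or sample-size target.

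**Inputs**
- Rule as written: support if the estimated OR exceeds 1 (The first choice of analyses, both hypotheses).
- Interval: 95% (same sentence). Two-sided is assumed, since sidedness is not stated.
- Direction: higher exposure, higher risk (Hypotheses). A rule based on the interval therefore looks only at the lower limit.
- Model: logistic regression with the three exposures mutually adjusted, plus sex and age (The first choice of analyses; the adjuster after sex is not named in the hypothesis-two paragraph).

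**Step 1: the rule as written, true OR = 1.** The estimated log OR is approximately normal around 0.
P(estimated OR > 1) = 1 − Φ(0) = 0.50.

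**Step 2: a rule based on the interval, true OR = 1.** The lower limit exceeds 1 when the estimated log OR exceeds 1.96 standard errors.
P(lower 95% limit > 1) = 1 − Φ(1.96) = 0.025.

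**Step 3: do these values depend on sample size or correlated exposures?** Null logistic regressions were simulated with three correlated exposures (assumed underlying correlation 0.4, one exposure skewed), sex and age. There were 2,500 runs for the first row and 4,000 for each of the others. The ranges are over the three exposures.

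| n (assumed) | Case proportion (assumed) | OR > 1 | Lower 95% limit > 1 |
|---|---|---|---|
| 4,000 | 8% | 48.2% to 50.4% | 2.5% to 3.1% |
| 1,000 | 6% | 47.8% to 51.7% | 2.7% to 2.8% |
| 300 | 40% | 49.8% to 51.0% | 2.3% to 2.9% |
| 100 | 40% | 48.8% to 49.8% | 2.3% to 2.6% |

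The values 50% and 2.5% hold closely throughout, so they need no case counts.

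**Step 4: can the interval width be stated for this study?** Approximately, SE = 1/√[n·p·(1 − p)·(1 − R²)] for an OR per SD, where p is the case proportion and R² the share of the exposure explained by the other covariates. The largest OR above 1 whose interval still includes 1 is exp(1.96·SE). Purely hypothetical inputs give:
- n = 994 with 50 cases: n·p·(1 − p) = 50 × (1 − 50/994) = 47.5. With R² = 0.2, SE = 1/√38.0 = 0.162 and the OR is 1.37. With R² = 0.6, SE = 1/√19.0 = 0.229 and the OR is 1.57.
- n = 4,000 with 8% cases: n·p·(1 − p) = 294.4. With R² = 0.2, SE = 1/√235.5 = 0.065 and the OR is 1.14. With R² = 0.6, SE = 1/√117.8 = 0.092 and the OR is 1.20.

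The first setting is of the order of the 1,094 follow-up interviews and the second of the 4,288 questionnaires (Study population). The plan gives no case counts, no R² and no unit for the OR. The answer moves from 1.14 to 1.57 on assumed inputs alone, so no width can be attributed to this study.

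**The case against.** The strongest reply is that the clause is only a direction key. It sits in a sentence that makes the interval part of the measure, the hypotheses are directional, and to support a hypothesis is weaker than to confirm it. On that reading the interval would be read in the usual way and no 50% rule exists. This is plausible and cannot be excluded. What remains is that the plan does not say so, and no other sentence gives the interval a role.

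A second reply is that the objective is exploratory, so no threshold is needed. That stands: estimation without a threshold is legitimate. It does not settle what the clause means, since the plan still speaks of supporting a hypothesis.

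Third, the contrast of 50% with 2.5% is generic: any sign rule and any two-sided 95% interval give it. That is true, and it is put forward here only as the meaning of the literal text.

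A reader might go further, multiply 50% by the number of planned ORs, and infer a count of false supports. The documents do not support this. The FSD definitions apply only if cases suffice, so the number of ORs is not fixed, and nothing indicates what share would be null. The Background reports strong cross-sectional associations for all three exposures. That does not establish prospective effects, but it makes an all-null scenario an extreme bound. A reader might also infer wide intervals throughout from the 1,094 interviews. Yet those serve only interview-defined Bodily Distress Syndrome; the other definitions use questionnaires ("Participants with irritable bowel, chronic widespread pain, and chronic fatigue will be defined with questionnaires"), with 4,288 at follow-up. Multiplicity across exposures and definitions is a separate disclosure point.

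**Conclusion.** The point holds as an unclear criterion, and it is minor. The plan's only statement of support refers to an OR above 1, and the 95% interval has no stated role in it. Taken literally, a truly null OR counts as support about 50% of the time, against 2.5% if the lower limit must exceed 1.

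The figures rest on an approximately normal estimate, a two-sided interval, and support counted only in the hypothesised direction. They describe the literal rule. They do not show that the authors intend to use it, and they are not a forecast of errors in this study. Because the intervals will be published with the ORs, readers will be able to see imprecision; the risk is over-worded conclusions.

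**What to change.** In both paragraphs of The first choice of analyses, replace the clause with one of the following.

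- If a criterion is intended: *an OR above 1 is the hypothesised direction; the hypothesis is regarded as supported for an exposure and FSD definition only if the lower limit of the 95% CI exceeds 1.*
- If pure estimation is intended, which the exploratory objective would justify: *an OR above 1 is the expected direction only; conclusions rest on the estimate with its 95% CI.*

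Either is adequate. Add that the same convention applies to the second and third choices of analyses.

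The cost is one clause in two places and one sentence, with no new data or models. The downside is that fewer associations will be called supportive.
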